6.3.2. Open Label Visits (Visit Window ± 7 days)

6.3.2.1. Week 60

- Symptom directed physical exam
- Body weight
- Vital signs: blood pressure, pulse, respiration rate, and temperature
- Review concomitant medications
- Review adverse events
- Perform study drug accountability
- Dispense open label study drugs
- Fasting blood sample for metabolic assessment (glucose and lipid panel [total cholesterol, HDL, direct LDL, and triglycerides]) no food or drinks, except water, at least 8 hours prior to blood collection
- Blood sample for serum chemistry and liver function tests, hematology, plasma HBV DNA, serum HBsAg (quantitative), HBV serology (qualitative HBsAg and HBeAg) virology (resistance surveillance), PPD
- Estimated creatinine clearance (using the Cockcroft-Gault method)
- Urine sample for urinalysis, pregnancy test (for females of child-bearing potential; in case of a positive urine test, a serum pregnancy test will be done). PPD

6.3.2.2. Week 72

- Complete physical examination with vital signs (blood pressure, pulse, respiration rate and temperature) and body weight
- DXA scan of hip and spine (within \pm 14 days of the expected visit date)
- Review concomitant medications
- Review adverse events
- Perform study drug accountability
- Dispense open label study drugs

- Fasting blood sample for bone biomarkers and metabolic assessment (glucose and lipid panel [total cholesterol, HDL, direct LDL, and triglycerides]) no food or drinks, except water, at least 8 hours prior to blood collection
- Fasting urine sample for renal biomarkers
- Blood sample for serum chemistry and liver function tests, hematology, plasma HBV DNA, serum HBsAg (quantitative), HBV serology (qualitative HBeAg and HBsAg), virology (resistance surveillance), PPD
- Estimated creatinine clearance (using the Cockcroft-Gault method)
- Urine sample for urinalysis, pregnancy test (for females of child-bearing potential; in case of a positive urine test, a serum pregnancy test will be done). PPD

6.3.2.3. Week 96

- Complete physical examination with vital signs (blood pressure, pulse, respiration rate and temperature) and body weight
- ECG (subjects must rest quietly in the supine position for a minimum of 5 minutes prior to the recording)
- DXA scan of hip and spine (within \pm 14 days of the expected visit date)
- Review concomitant medications
- Review adverse events
- Perform study drug accountability (no study drug will be dispensed at Week 96 visit)

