6.5. Assessments for Premature Discontinuation from Study

If a subject discontinues study dosing (for example, as a result of an AE), every attempt should be made to keep the subject in the study and continue to perform the required study-related follow-up and procedures (see Section 6.6, Criteria for Discontinuation of Study Treatment). If this is not possible or acceptable to the subject or investigator, the subject may be withdrawn from the study.

The ED Visit should be performed within 72 hours (i.e., visit window is \pm 3 days) of the last study drug dose.

- Complete physical exam with vital signs (blood pressure, pulse, respiration rate and temperature) and body weight
- ECG (subjects must rest quietly in the supine position for a minimum of 5 minutes prior to the recording)
- DXA scan of spine and hip to be performed within ±14 days of the expected visit date and is done only if not done within the past 12 weeks of the ED visit
- Review concomitant medications
- Review adverse events
- Fasting blood sample for bone biomarkers and metabolic assessment (glucose and lipid panel [total cholesterol, HDL, direct LDL, and triglycerides]) no food or drinks, except water, at least 8 hours prior to blood collection (only collected if not done in the last 12 weeks)
- Fasting urine sample for renal biomarkers (only collected if not done in the last 12 weeks)
- Blood sample for serum chemistry and liver function tests, hematology, PT/INR, plasma HBV DNA, serum HBsAg (quantitative), HBV serology (qualitative HBsAg and HBeAg), virology (resistance surveillance), PPD
- Estimated creatinine clearance (using the Cockcroft-Gault method)
- Blood sample for Fibrotest[®]
- Child-Pugh Score (Assessment requires: total bilirubin, albumin, PT/INR, Ascites assessment, and Hepatic encephalopathy assessment)
- Urine sample for urinalysis, pregnancy test (for females of child-bearing potential; in case of a positive urine test, a serum pregnancy test will be done), PPD
- Health Related Quality of Life (HRQoL) Surveys (SF-36, WPAI and CLDQ) are done only if not done within the past 24 weeks of the ED visit

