8.1.3. Secondary Endpoint

The secondary efficacy endpoints are:

- The proportion of subjects with HBV DNA ≥ 20 IU/mL (as determined by the modified US FDA-defined snapshot algorithm) at Week 96
- The proportion of subjects with HBV DNA < 20 IU/mL and target detected/not detected (i.e. < LLOD) at Weeks 48 and 96, as determined by the modified US FDA-defined snapshot algorithm
- The proportion of subjects with HBeAg loss and proportion with seroconversion to anti-HBe at Weeks 48 and 96

- The proportion of subjects with HBsAg loss and proportion with seroconversion to anti-HBs at Weeks 48 and 96
- The proportion of subjects with normal ALT and proportion with normalized ALT (by central laboratory and AASLD criteria) at Weeks 48 and 96
- The change from baseline in fibrosis as assessed by FibroTest[®] at Weeks 48 and 96

The key secondary safety endpoints are:

- The percent change from baseline in hip bone mineral density (BMD) at Week 48
- The percent change from baseline in spine bone mineral density (BMD) at Week 48
- The change from baseline in eGFR_{CG} (measured by Cockcroft-Gault method) at Week 48

The secondary safety endpoints are:

- The percent change from baseline in hip bone mineral density (BMD) at Week 96
- The percent change from baseline in spine bone mineral density (BMD) at Week 96
- The change from baseline in eGFR_{CG} (measured by Cockcroft-Gault method) at Week 96

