3.6.2. Analysis Windows

Subject visits might not occur on protocol specified days. Therefore, for the purpose of analysis, observations will be assigned to analysis windows.

The following windows (Table 3-1 to Table 3-6) apply only to baseline and postbaseline on-treatment assessments collected during the double-blind phase and open-label phase. For summaries and analyses, assessments will first be categorized into baseline and postbaseline on-treatment assessments occurring during the double-blind or open-label phase before applying analysis windows.

Baseline value for the double-blind phase is defined as the last nonmissing value obtained on or prior to Study Day 1. For DXA BMD, it is defined as the last value on or prior to Study Day 14.

For subjects who completed blinded study drug and entered the open-label phase, laboratory assessments that occurred during the period from Study Day 2 up to and including the minimum of the Last Dose Date of Blinded Study Drug + 3 days and Open-label Study Day 1, will be considered as postbaseline on-treatment assessments during the double-blind phase. If a subject prematurely discontinued blinded study drug or did not enter open-label phase after completion of blinded study drug, then postbaseline on-treatment assessments during the double-blind phase will be defined as assessments that occurred during the period from Study Day 2 up to and including the Last Dose Date of Blinded Study Drug + 3 days. DXA assessments that occurred during the period from Study Day 15 up to and including the Last Dose Date of Blinded Study Drug + 14 days will be considered as postbaseline on-treatment assessments during the double-blind phase.

Baseline value for the open-label phase is defined as the last nonmissing value obtained on or prior to Open-Label Study Day 1. For DXA BMD, it is defined as the last value on or prior to Open-Label Study Day 14.

For subjects who entered the open-label phase, postbaseline on-treatment assessments during the open-label phase will be defined as assessments that occurred during the period from Open-label Study Day 2 up to the Last Dose Date + 3 days. DXA assessments that occurred during the period from Open-label Study Day 15 up to the Last Dose Date + 14 days will be considered as postbaseline on-treatment assessments during the open-label phase.

Baseline value for the TFFU phase is defined as the last nonmissing value obtained on or prior to the Last Dose Date + 3 days.

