7. SAFETY ANALYSES

For the final analysis, cumulative safety data (treatment-emergent AEs, treatment-emergent laboratory abnormalities, etc.) will be summarized for (1) subjects in the FAS during the double-blind phase, (2) subjects in the Open-Label Safety Analysis Set during the open-label phase, and (3) subjects in the TFFU Safety Analysis Set during the TFFU phase. Exposure data will be summarized for (1) and (2).

By-visit summary tables of safety measurements will be presented for the entire study treatment period (double-blind and open-label phase combined) based on subjects in the Safety Analysis Set from baseline to Week 96, and open-label phase based on subjects in the Open-Label Safety Analysis Set from open-label baseline to Week 96. Statistical comparisons will only be performed for the analysis of the entire study treatment period, unless otherwise specified. No by-visit summaries for safety measurements will be generated for the TFFU phase.

All safety data including data collected during the treatment-free follow-up period will be included in data listings.

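### If the Week 96 DXA window runs from the nominal visit date, a compliant scan can fall up to 21 days (22 at most) after the last dose, past the SAP's open-label limit of last dose + 14 days

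*SAP*

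**What the plan says.** **Protocol, timing.** Section 6.3.2 gives open-label visits a window of ±7 days. At Week 96 (6.3.2.3) the DXA scan may be done within ±"14 days of the expected visit date", and "no study drug will be dispensed at Week 96 visit". The last dose therefore falls on or before the day of the visit. The protocol neither defines the expected visit date nor fixes the last dose day relative to the Week 96 visit.

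**SAP, on-treatment rule.** Section 3.6.2 accepts as open-label on-treatment only "DXA assessments that occurred during the period from Open-label Study Day 15 up to the Last Dose Date + 14 days". Other open-label assessments get last dose + 3 days. The order of operations is explicit: "assessments will first be categorized into baseline and postbaseline on-treatment assessments occurring during the double-blind or open-label phase before applying analysis windows".

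**SAP, visit windows.** Table 3-4 sets nominal Day 672 for Week 96 with a window of Days 589 to 840. The Week 72 window ends on Day 588.

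**Endpoint.** Protocol 8.1.3 lists among the secondary safety endpoints "The percent change from baseline in hip bone mineral density (BMD) at Week 96", and the same for spine. Neither is key secondary. On data after treatment, SAP 7 states: "No by-visit summaries for safety measurements will be generated for the TFFU phase". It does keep follow-up data in the listings.

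**The concern.** The + 14 days in the SAP is the same number as the protocol's DXA tolerance, so the rule looks meant to retain late but compliant scans. It does that when the visit takes place on or after its expected date and the last dose is on the visit day. It makes no allowance for an early visit, which moves the last dose forward while the end of the scan window stays where it is.

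A scan that fails the on-treatment test never reaches Table 3-4, so the wide Week 96 window cannot recover it. Nothing takes its place:

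- a Week 72 scan done on schedule belongs to the window ending on Day 588;
- SAP 3.4.1 does not impute missing values in general;
- the last-observation-carried-forward analysis in Protocol 8.3 covers only the key secondary safety endpoints, which are Week 48 measures;
- the treatment-free follow-up phase has no by-visit safety summaries.

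The subject would be missing for Week 96 hip and spine BMD despite an end-of-study scan done when the protocol allowed.

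**Working it through.** **Inputs.** Visit offset from the expected date: v = −7 to +7 days (Protocol 6.3.2). Scan offset from the expected date: d = −14 to +14 days (Protocol 6.3.2.3). Nominal Week 96: Day 672 (SAP Table 3-4). Limit: last dose + 14 days (SAP 3.6.2). The last dose is b days before the visit. The documents do not state b, so I take b = 0 and show b = 1 as well.

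**1. The SAP's own figure.** With the scan window counted from the nominal date,

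gap = scan day − last dose day = d − v + b.

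For a visit on time (v = 0), b = 0 and the latest scan (d = 14), the gap is 14 − 0 + 0 = 14 days, which equals the SAP limit.

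**2. Worst case, nominal reading.** The earliest visit is Day 672 − 7 = 665. The latest scan is Day 672 + 14 = 686. The gap is 686 − 665 = 21 days for b = 0 and 22 days for b = 1. Day 686 lies inside the Table 3-4 window of 589 to 840, so it is the on-treatment test that removes the scan.

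**3. When a scan is lost (b = 0).** The condition is d − v > 14. Since d is at most 14, v must be −1 or lower. Since v is at least −7, d must be 8 or higher. Both are necessary, and together they must exceed 14 days: a visit 7 days early loses scans at d = 8 to 14, while a visit 1 day early loses only d = 14. If the visit is on or after the expected date, nothing is lost.

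**4. Date combinations.** There are 15 × 29 = 435 pairs of v and d.

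| Scan window counted from | Last dose | Largest gap | Pairs beyond + 14 |
|---|---|---|---|
| Nominal date | visit day | 21 days | 7+6+5+4+3+2+1 = 28 |
| Nominal date | day before | 22 days | 8+7+6+5+4+3+2+1 = 36 |
| Actual visit | visit day | 14 days | 0 |
| Actual visit | day before | 15 days | 15 (d = 14 at each v) |

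The first row is 28/435 = 6.4% of the grid. This counts possible date pairs and does not estimate how often they occur.

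**5. Which reading.** At Week 48 (Protocol 6.3.1.6) the visit window and the DXA window are both −14 days, the latter again counted from the expected visit date. Identical windows suggest a common nominal anchor. This favours the nominal reading without settling it.

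**6. Blinded phase.** At Week 48 the earliest visit is Day 336 − 14 = 322 and the latest scan is Day 336. With the last dose on the visit day the gap is 14 days, which the existing blinded limit covers.

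**7. Scale, as context only.** No Week 96 power is stated. Under the Week 48 assumptions (Protocol 8.9), the SD is √((2.71² + 2.83²)/2) = 2.77 for hip and √((3.84² + 4.14²)/2) = 3.99 for spine, and power = Φ(δ/(SD·√(2/n)) − 1.96). At n = 230 per arm, with δ = 1.81 and 2.00, power is above 99.9% for both, in line with the stated > 99%. With 20% of scans lost (n = 184) it is above 99.9% for hip and 99.8% for spine.

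**The case against.** **The strongest case against** is that timing within a visit schedule does not make a scan on-treatment. Protocol 8.7 summarises safety data only up to the last dose, and Protocol 8.2.1.3 handles follow-up data separately. The SAP's + 14 days is already more generous, and its limits of + 3 and + 14 days track protocol windows, which suggests a deliberate rule. Part of this stands: the protocol does not clearly promise that late scans will be analysed. But the SAP has already gone past the last dose for DXA, apparently to fit the scan tolerance, and it nowhere says that compliant later scans are excluded on purpose.

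**The consequence is limited, and that stands in full.** The endpoint is outside the testing sequence in Protocol 8.4. SAP 7.3.1 describes mean percent change without a test, although it does compare BMD status and change categories between arms. Both arms take TAF by then, and no mechanism for differential loss is apparent.

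**Stronger readings that a reader might infer, and why they fail:**

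- *That valid scans are discarded as a matter of course.* The scans stay in the listings, and loss needs a particular combination of dates.
- *That about 15 subjects per arm are lost (6.4% of 230).* This assumes uniform, independent visit and scan dates and no dropout by Week 96. The documents have no data on scan timing.
- *That early-discontinuation scans are lost up to last dose + 17.* Protocol 6.5 asks for a "DXA scan of spine and hip to be performed within ±14 days of the expected visit date". Reaching + 17 means counting 14 days from a visit actually held 3 days after the last dose, whereas the 21-day result counts from a nominal date. If the target is the last dose itself, the maximum is 14. Such scans before Day 589 would not belong to the Week 96 window in any case.
- *That the blinded limit also needs + 21.* The Week 48 windows do not support it. For subjects who continue, open-label post-baseline DXA starts on open-label Day 15, so a longer blinded limit could overlap with it.

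**Conclusion.** The mismatch holds, conditionally. If the expected visit date is nominal Day 672, a Week 96 scan within the protocol windows can fall 15 to 21 days after a last dose taken on the visit day (up to 22 if it was the day before) and be left out of the Week 96 hip and spine BMD summaries. If the window runs from the actual visit, nothing is lost with the last dose on the visit day, and the overrun is at most one day otherwise.

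The number of subjects affected cannot be derived from the documents and is probably small. The primary endpoint and the key secondary Week 48 BMD endpoints are not touched by this open-label rule. The point is worth correcting because the loss is avoidable and the measure changes slowly. It does not threaten the trial's conclusions.

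**What to change.** In SAP 3.6.2, for the open-label phase only:

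1. State what the expected visit date means for the Week 96 DXA scan.
2. Change the DXA on-treatment limit to Last Dose Date + 22 days, or + 21 if the last dose is taken on the visit day. By steps 2 and 4 of the working, + 22 covers every scan within the protocol windows when the last dose is on the visit day or the day before.
3. Report by arm how many Week 96 scans fall beyond + 14 days, and repeat the Week 96 BMD summaries without them as a sensitivity analysis.
4. Leave the blinded limit at + 14 days.

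The cost is one number in the SAP, the matching programming and one extra set of tables; no new data are needed. SAP 1 already provides for changes after finalisation to be documented in the study report. The downside is small: a few scans would be about a week further from the last dose of study drug. Some might follow the start of another HBV therapy, whose use after stopping is encouraged in Protocol 3.1. The sensitivity analysis shows whether that matters.

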The analysis windows for fasting renal biomarkers including urine retinol binding protein (RBP), urine RBP to creatinine ratio, urine beta-2-microglobulin (B2M), urine B2M to creatinine ratio, and bone biomarkers including C-type collagen sequence (CTX), procollagen type 1 N-terminal propeptide (P1NP) are presented in Table 3-6.

Table 3-6. Analysis Windows for Fasting Renal and Bone Biomarkers

Visit ID	Nominal Day	Lower Limit	Upper Limit
Baseline			1
Week 4	28	2	56
Week 12	84	57	126
Week 24	168	127	252
Week 48	336	253	420

Visit ID	Nominal Day	Lower Limit	Upper Limit
Week 72	504	421	588
Week 96	672	589	840

Post-treatment assessments during the treatment free follow-up (TFFU) phase will be defined as assessments that occurred during the period after the Last Dose Date (LDD) + 3 days up to the Last Study Date.

The analysis windows for post-treatment assessments are presented in Table 3-7.

Table 3-7. Analysis Windows for Post-Treatment Assessments

Visit ID	Nominal Follow-Up Day	Lower Limit	Upper Limit
Follow-Up Week 4	28	LDD+4	42
Follow-Up Week 8	56	43	70
Follow-Up Week 12	84	71	98
Follow-Up Week 16	112	99	126
Follow-Up Week 20	140	127	154
Follow-Up Week 24	168	155	182

3.6.3. Selection of Data in the Event of Multiple Records in an Analysis Visit Window

Depending on the statistical analysis method, single values are required for each analysis window. For example, change from baseline by visit usually requires a single value, whereas a time-to-event analysis would not require one value per analysis window. When a single value is needed, the following rule(s) will be used.

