For baseline of the double-blind, open-label, and TFFU phases, the last available record on or prior to the first dose of blinded study drug, open-label study drug, and last dose date + 4 days will be selected, respectively. For DXA BMD baseline, the last value on or prior to Study Day 14 and Open-Label Study Day 14 will be selected for the double-bind and open-label phases, respectively. If there are multiple records with the same time or no time recorded on the same day for numeric observations, the average will be computed for that day, except for HBV DNA and quantitative HBsAg the geometric mean will be taken instead. If there are multiple records with the same time or no time recorded on the same day for categorical observations, the most conservative value will be taken, eg, negative will be selected over positive for HBeAg and HBsAg, and positive will be selected over negative for HBeAb and HBsAb.

The following specified rules will be used for postbaseline visits:

- **ALT:** The largest value will be included in the analysis when 2 or more ALT values occur within the same visit window.
- **BMD:** The latest record in the window will be selected
- **HBV DNA (IU/mL):** The record on the latest day in the window will be selected. If there is more than 1 record on the selected day, the geometric mean will be taken.
- Quantitative HBsAg (IU/mL): The record closest to the nominal day for that visit will be selected. If there are 2 records equidistant from the nominal day, the latest will be selected. If there is more than 1 record on the selected day, the geometric mean will be taken.
- **Serology:** For HBeAg, HBeAb, HBsAg, and HBsAb, the record closest to the nominal day for that visit will be selected. If there are 2 records equidistant from the nominal day, the latest will be selected. If there is more than 1 record on the selected day, the most conservative value will be taken, ie, positive will be selected over negative for HBeAg and HBsAg, and negative will be selected over positive for HBeAb and HBsAb.

For all other laboratory parameters:

• If multiple valid non-missing **numeric** observations exist in a window, then records will be chosen as follows:

The record closest to the nominal day for that visit will be selected. If there are 2 records equidistant from the nominal day, the latest will be selected. If there is more than 1 record on the selected day, the average will be taken.

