FibroTest score will be summarized using descriptive statistics (sample size, mean, SD, median, Q1, Q3, minimum, and maximum) by treatment group for subjects in the FAS. The p-value, differences in change from baseline in FibroTest score between the 2 treatment groups and the associated 95% CI will be constructed using ANOVA models, including treatment group, baseline HBeAg status (HBeAg-positive or HBeAg-negative) and age (< 50 or ≥ 50 years) as fixed effects in the model. A shift table of fibrosis stage from baseline based on the FibroTest score at Week 24, 48, and 96 will be provided. Mean change from baseline in FibroTest score will be plotted with 95% CI over time using observed data from baseline to Week 96. A listing of fibrosis assessment by FibroTest will also be provided.

All the analyses of the secondary efficacy endpoints, using both the M F and the M E approach, and plots described above will be repeated for subjects in the Open-Label FAS from open-label baseline to Week 96. No statistical comparisons will be performed.

For subjects in the TFFU FAS, only HBV DNA, ALT, HBsAg, HBeAg loss/seroconversion, and HBsAg loss/seroconversion endpoints will be summarized by visit in the TFFU phase as described above only using the M E approach. No statistical comparisons will be performed.

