7.1.6. Treatment-Emergent AEs

7.1.6.1. Definition of Treatment-Emergent

Treatment-emergent AEs will be separately defined for the double-blind phase and the open-label phase. Post-treatment-emergent AEs will be defined only for the TFFU phase.

Treatment-emergent AEs occurring during the double-blind phase are defined as:

- Any AE with onset date on or after the blinded study drug start date and no later than the minimum of the blinded study drug stop date + 3 days and the day prior to the first dose date of open-label study drug, if applicable, for those who discontinued blinded study drug permanently, or
- Any AE with onset date on or after the blinded study drug start date for those who are still on the blinded study drug, or
- Any AE leading to blinded study drug discontinuation.

Treatment-emergent AEs occurring during the open-label phase are defined as:

- Any AE with onset date on or after the open-label study drug start date and no later than the open-label study drug stop date + 3 days for those who discontinued open-label study drug permanently, or
- Any AE with onset date on or after the open-label study drug start date for those who are still on open-label study drug, or
- Any AE leading to open-label study drug discontinuation.

Post-treatment-emergent AEs occurring during the TFFU phase are defined as:

Any AE with onset date after the last dose of study drug + 3 days

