7.2.2.1. Treatment-Emergent Laboratory Abnormalities

Treatment-emergent laboratory abnormalities occurring in the double-blind phase are defined as values that increase by at least 1 toxicity grade from baseline at any postbaseline visit up to and including the minimum of the blinded study drug stop date + 3 days and the first dose date of open-label study drug, if applicable, for those who discontinued blinded study drug permanently, or values that increase by at least 1 toxicity grade from baseline at any postbaseline visit for those who are still on double-blind study drug. If the relevant baseline laboratory value is missing, any laboratory abnormality of at least Grade 1 observed within the double-blind phase will be considered treatment emergent.

Treatment-emergent laboratory abnormalities occurring in the open-label phase are defined as values that increase by at least 1 toxicity grade from open-label baseline at any open-label postbaseline visit up to and including the last dose date of the open-label study drug + 3 days for those who discontinued open-label study drug permanently, or values that increase by at least 1 toxicity grade from open-label baseline at any open-label postbaseline visit for those who are still on open-label study drug. For the analyses of abnormalities occurring during open-label treatment, open-label baseline will be the last available record on or prior to Open-Label Study Day 1.

Post-treatment-emergent laboratory abnormalities occurring in the TFFU phase are defined as values that increase by at least 1 toxicity grade from TFFU baseline. For the analyses of abnormalities occurring during the TFFU phase, TFFU baseline will be the last available record on or prior to last dose date + 3 days.

Fasting glucose and nonfasting glucose (including glucose results without a known fasting status) are graded based on different grading scales as specified in the protocol. Treatment-emergent and post-treatment-emergent laboratory abnormalities will be summarized for fasting glucose. Since nonfasting glucose was not assessed at baseline, the maximum postbaseline grade will be summarized.

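### SAP 3.6.3 takes the treatment-free follow-up baseline up to last dose + 4 days, but the two other definitions stop at + 3 days, so a record on day + 4 qualifies as both baseline and follow-up

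*SAP*

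**What the plan says.** **Record-selection rule.** SAP 3.6.3 gives the cut-off for the baseline record in each of the three phases in one sentence. The part for TFFU reads "and last dose date + 4 days will be selected, respectively", and the cut-off day is included.

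**The two other definitions of the same baseline.**
- SAP 3.6.2: the baseline value for the "TFFU phase is defined as the last nonmissing value obtained on or prior to the Last Dose Date + 3 days".
- SAP 7.2.2.1, for laboratory abnormalities: "TFFU baseline will be the last available record on or prior to last dose date + 3 days".

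**Where follow-up begins.** SAP 3.6.2 defines post-treatment assessments as "assessments that occurred during the period after the Last Dose Date (LDD) + 3 days up to the Last Study Date". Table 3-7 accordingly opens Follow-Up Week 4 at LDD+4 and closes it on follow-up day 42. The adverse event rule in SAP 7.1.6.1 uses the same boundary: "Any AE with onset date after the last dose of study drug + 3 days".

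**What uses the TFFU baseline.** SAP 6.2.2 says that "only HBV DNA, ALT, HBsAg, HBeAg loss/seroconversion, and HBsAg loss/seroconversion endpoints will be summarized by visit in the TFFU phase", with missing data excluded and no statistical comparisons. SAP 6.2.1 puts the TFFU baseline in place of baseline in the definitions of antigen loss, seroconversion and ALT normalization. SAP 3.1.10.1 and 3.1.10.2 admit subjects to the TFFU serologically evaluable sets by their antigen and antibody status at TFFU baseline.

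**The concern.** A baseline should end where the follow-up it is compared with begins. Every other rule in the SAP that touches this boundary keeps days up to + 3 on one side and days from + 4 on the other. SAP 3.6.3 alone reaches one day into follow-up, and no text explains why.

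Two programmers working from different sections could pick different baseline records for the same subject. Under 3.6.3, any change in ALT or HBsAg that has occurred by day + 4 becomes part of the baseline, so the reported off-treatment change omits it. A change in serologic status by day + 4 could also alter whether the subject is counted as evaluable for loss or seroconversion.

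Such a record is plausible. Protocol 6.5 asks for the early discontinuation visit within 72 hours of last dose, so a visit one day late falls on day + 4. The Week 96 visit has a window of ± 7 days (Protocol 6.3.2) around its scheduled date, not around last dose.

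**Working it through.** The plan states no figure to reproduce. The check compares day intervals. Let d = visit date minus last dose date, which is how SAP 3.6.1 counts follow-up days.

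| Rule | Source | Days covered |
|---|---|---|
| TFFU baseline, record selection | SAP 3.6.3 | d ≤ 4 |
| TFFU baseline, definition | SAP 3.6.2 | d ≤ 3 |
| TFFU baseline, laboratory abnormalities | SAP 7.2.2.1 | d ≤ 3 |
| Post-treatment assessments | SAP 3.6.2 | d > 3 |
| Follow-Up Week 4 | SAP Table 3-7 | 4 ≤ d ≤ 42 |

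**Overlap as written.** The days that satisfy both d ≤ 4 and 4 ≤ d ≤ 42 are d = 4 only, so one day overlaps.

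**Overlap with + 3.** No day satisfies both d ≤ 3 and 4 ≤ d ≤ 42. The last baseline day is 3 and the first follow-up day is 4, so there is no gap either.

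**When the day-4 record is the analysed Week 4 value.** SAP 3.6.3 sets this by parameter.
- Quantitative HBsAg and serology take the record closest to nominal day 28. Day 4 is 28 − 4 = 24 days away. Of the other days in the window, the furthest is day 5, at 28 − 5 = 23; day 42 is 42 − 28 = 14 away. Any other record in the window therefore displaces day 4, which is selected only if it stands alone.
- HBV DNA: "The record on the latest day in the window will be selected". Day 4 is the first day of the window, so again it is selected only if it stands alone.
- ALT takes the largest value, so day 4 is selected if it stands alone or is the highest.

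**Effect on change from baseline.** Take a subject with records at d = 2, 4 and 28, with ALT values A2, A4 and A28, and log10 HBsAg values B2, B4 and B28.

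| | Baseline under + 3 | Change under + 3 | Baseline under + 4 | Change under + 4 |
|---|---|---|---|---|
| ALT | A2 | max(A4, A28) − A2 | A4 | max(A4, A28) − A4 |
| log10 HBsAg | B2 | B28 − B2 | B4 | B28 − B4 |

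The two rules differ by A4 − A2 for ALT and B4 − B2 for log10 HBsAg, that is, by the change from day 2 to day 4. Change after day 4 is still measured under either rule. Under + 4 the ALT change is zero if A4 ≥ A28, and it cannot be negative, because the baseline value is itself among those from which the maximum is taken. If the day-28 record is missing, the + 4 rule gives A4 − A4 = 0 and B4 − B4 = 0, against A4 − A2 and B4 − B2 under + 3.

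**The case against.** The strongest reply is that SAP 3.6.2 is the definition, SAP 7.2.2.1 agrees with it, and 3.6.3 only settles which record to use when there are several. On that view the + 4 is a slip that a careful programmer would override. This is fair as to intent. It does not remove the conflict: 3.6.3 states its own cut-off, applies whenever a single value is needed, and nothing in the SAP ranks 3.6.2 above it.

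The objections about consequences stand, and they limit the point. A reader might infer the following, which the documents do not support.

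- **That post-treatment-emergent grades are understated.** SAP 7.2.2.1 sets its own + 3 cut-off for laboratory abnormalities, and that specific rule governs them.
- **That an HBV DNA rise is hidden by entering the baseline.** SAP 6.2.2 analyses HBV DNA as proportions above or below 20 IU/mL. A proportion at a follow-up visit does not use the baseline value. Change from baseline is planned there for log10 HBsAg and ALT, not HBV DNA.
- **That the Week 4 change is always zero, or wholly wrong.** Zero requires the day-4 record to be the one selected. Follow-up visits are planned every 4 weeks, so a later record will usually be available, and only change up to day 4 can be lost.
- **That three rival baseline definitions use + 3.** Two do. The third + 3 rule sets where follow-up starts.

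The reach is also narrow. An early discontinuation visit on day + 4 is already outside the protocol's timing. SAP 7 and 7.2.1 plan no by-visit safety or numeric laboratory summaries for TFFU, and SAP 7.2.3 summarizes ALT elevations for the open-label phase only.

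**Conclusion.** The inconsistency is real and the rule is wrong as written: one day, LDD+4, lies on both sides of the TFFU baseline boundary. The correction is minor.

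The outputs that can change are descriptive: ALT change and normalization, log10 HBsAg change, HBeAg and HBsAg loss and seroconversion, and membership of the TFFU serologically evaluable sets. They change only for a subject with a record dated exactly LDD+4, and only if that record differs from the one that + 3 would select. The primary and key secondary endpoints and the Week 96 comparisons do not use the TFFU baseline.

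This rests on two assumptions: that the cut-off in 3.6.3 is inclusive, as worded, and that 3.6.3 might be programmed literally. The documents show neither which cut-off was programmed nor how many subjects have such a record, so no overall effect can be calculated.

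**What to change.** In SAP 3.6.3, change the TFFU cut-off from last dose date + 4 days to last dose date + 3 days, or replace it with a reference to the definition in SAP 3.6.2. Either brings it into line with SAP 3.6.2, Table 3-7 and SAP 7.2.2.1, and leaves no overlap and no gap.

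The SAP is marked final, and SAP 1 requires later changes to be documented in the CSR. The sponsor should therefore confirm which cut-off the TFFU baseline program uses, list any subjects with a record on LDD+4, rerun the TFFU summaries if + 4 was used, and note the correction in the CSR. The cost is one character of text and one program check, with no new data and no effect on trial conduct.
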